8.1.6. Solicited adverse events

8.1.6.1. Solicited local (injection-site) adverse events

The following local (injection-site) AEs will be solicited:

Table 11 Solicited local adverse events

Pain at injection site
Redness at injection site
Swelling at injection site

If subjects/subject's parent(s)/LAR(s) observe any large injection site reaction, they should contact the study personnel to determine if a visit to the investigator's office for evaluation is necessary.

A large injection site reaction is:

- a swelling that measures more than 100 mm across where the vaccine was given, or
- a noticeable irregular/uneven swelling where the vaccine was given, or

- a noticeable increase in size of the arm that interferes with or prevents everyday activities (e.g., writing, use of computer, school attendance, sleeping, etc.).

In case of questions or uncertainties, the subject/subject's parent(s)/LAR(s) should contact the investigator by phone and the investigator will determine whether or not a visit should be arranged.

The investigator will record detailed information describing the AE on a specific large injection site reaction screen in the eCRF. An SAE report should also be completed if the large injection site reaction meets the definition of SAE.

8.1.6.2. Solicited general adverse events

The following general AEs will be solicited:

Table 12 Solicited general adverse events

Fatigue
Fever*
Gastrointestinal symptoms †
Headache

^{*} The preferred route for temperature measurement is oral. Fever is defined as: ≥37.5°C for oral, axillary or tympanic route, or ≥38.0°C for the rectal route.

Note: Temperature will be recorded in the evening. Should additional temperature measurements be performed at other times of day, the highest temperature will be recorded in the eCRF.

8.1.7. Clinical laboratory parameters and other abnormal assessments qualifying as adverse events or serious adverse events

In absence of diagnosis, abnormal laboratory findings (e.g. clinical chemistry, haematology, urinalysis) or other abnormal assessments (e.g. medical imaging) that are judged by the investigator to be clinically significant will be recorded as AE or SAE if they meet the definition of an AE or SAE (refer to Sections 8.1.1 and 8.1.2). Clinically significant abnormal laboratory findings or other abnormal assessments that are present at baseline and significantly worsen following the start of the study will also be reported as AEs or SAEs. However, clinically significant abnormal laboratory findings or other abnormal assessments that are associated with the disease being studied, unless judged by the investigator as more severe than expected for the subject's condition, or that are present or detected at the start of the study and do not worsen, will not be reported as AEs or SAEs.

The investigator will exercise his or her medical and scientific judgement in deciding whether an abnormal laboratory finding or other abnormal assessment is clinically significant.

[†]Gastrointestinal symptoms include nausea, vomiting, diarrhoea and/or abdominal pain.

8.1.8. Adverse events of specific interest

AEs of specific interest for safety monitoring include the occurrence of

- NOCIs such as autoimmune disorders, asthma, type 1 diabetes and allergies. Refer to Section 8.1.8.1 for a non-exhaustive list of illnesses that can be recorded as NOCIs.
- GBS (to be reported as an SAE).
- Meningococcal disease (to be reported as an SAE).

See Section 8.2 and 8.3 for information on recording and reporting of these events.

8.1.8.1. List of New Onset of Chronic Illnesses

Table 13 presents a non-exhaustive list of illnesses that can be recorded as NOCIs.

Table 13 List of NOCIs

Disease/Disorder	
Blood autoimmune disorders	Anaemia haemolytic autoimmune Antiphospholipid syndrome Cold type haemolytic anaemia Coombs positive haemolytic anaemia Idiopathic thrombocytopenic purpura Pernicious anaemia Warm type haemolytic anaemia Autoimmune thrombocytopenia Evan's syndrome Autoimmune neutropenia Thrombocytopenias
Endocrine autoimmune disorder	Basedow's disease Insulin autoimmune syndrome Polyglandular autoimmune syndrome type I Polyglandular autoimmune syndrome type II Autoimmune thyroiditis Diabetic mastopathy Lymphocytic hypophysitis Polyglandular autoimmune syndrome type III
Endocrine symptoms	Hyperthyroidism Hypothyroidism Goiter
Hepatic autoimmune disorder	Autoimmune hepatitis Biliary cirrhosis primary
Muscular autoimmune disorder	Myasthenia gravis Myasthenia gravis neonatal Polymyalgia Polypyalgia rheumatica Polymyositis Ocular myasthenia Myasthenia gravis crisis

64

[figure not shown]
C0921004 (MenACWY-TT-100 EXT:027 Y6,7,8,9,10, 200171)
Protocol Amendment 2

Disease/Disorder					
Lupus erythematosus and associated conditions	Lupoid hepatic cirrhosis				
, ,, , , , , , , , , , , , , , , , , , ,	Lupus encephalitis				
	Lupus nephritis				
	SLE arthritis				
	Systemic lupus erythematosus				
	Systemic lupus erythematosus rash				
	Lupus-like syndrome				
	Cutaneous lupus erythematosus				
	Lupus pneumonitis				
	Neonatal lupus erythematosus				
	Lupus vasculitis				
	Pericarditis lupus				
	Lupus endocarditis				
	Peritonitis lupus				
	Neuropsychiatric lupus				
Autoimmune disorders NEC	Ankylosis spondylitis				
	Cryoglobulinaemia				
	Gastritis atrophic				
	Goodpasture's syndrome				
	Keratoconjunctivitis sicca				
	Keratoderma blenorrhagica				
	Mixed connective tissue disease				
	Reiter's syndrome				
	Sicca syndrome				
	Sjogren's syndrome				
	Sympathetic ophtalmia				
	Leukoencephalomyelitis				
	Toxic oil syndrome				
	Cryofibrinogenaemia				
	Encephalitis allergic				
	Nephritis autoimmune				
	Acute haemorrhagic leukoencephalitis				
	Autoimmune disorder				
Rheumatoid arthritis and associated conditions	Felty's syndrome				
	Rheumatoid arthritis				
	Rheumatoid lung				
	Rheumatoid vasculitis				
	Rheumatoid nodule				
	Juvenile arthritis				
	Laryngeal rheumatoid arthritis				
Scleroderma and associated disorders	CREST syndrome				
Scieroderma and associated disorders	CREST syndrome Morphoea Scleroderma Systemic sclerosis Systemic sclerosis pulmonary Scleroderma renal crisis				

25-FEB-2016 65

Disease/Disorder	
Skin autoimmune disorders NEC	Benign familial pemphigus
	Dermatitis herpetiformis
	Dermatomyosistis
	Eosinophilic fasciitis
	Herpes gestationis
	Linear IgA disease
	Pemphigoid
	Pemphigus
	Vitiligo
Acute and chronic thyroiditis	Thyroiditis
·	Thyroiditis acute
	Thyroiditis chronic
	Thyroiditis subacute
	Autoimmune thyroiditis
Optic neuritis	Optic neuritis
·	Optic neuritis retrobulbar
	Vision blurred
	Blindness
	Visual acuity reduced
	Visual evoked potential abnormality
Multiple sclerosis	Multiple sclerosis
	Demyelinating disorder
	Gait disturbances
	Muscle weakness
	Paraesthesias
	(Cognitive impairment)
	(Nuclear magnetic resonance imaging brain abnormal)
Transverse myelitis	Myelitis Transverse
	Muscle weakness
	Low back pain
	Paraesthesias and dysaesthesias
	Paralysis
	(Urinary retention)
	(Neurogenic bladder)
Guillain-Barre syndrome	Guillain-Barre syndrome
	Muscle weakness
	Paraesthesias and dysaesthesias
Diabetes mellitus insulin-dependent	Diabetes mellitus
	Diabetes mellitus (incl. subtypes)
	Glucose metabolism disorders (incl. diabetes mellitus)
Uveitis	Uveitis
	Eye pain
	Eye redness
	Photophobia
Glomerulonephritis	Lupus nephritis
	Proteinuria
	Haematuria
	Glomerular filtration rate decreased
	(Hypoproteinemia)
	(Oedema)
	Blood urea increased
	Blood creatinine increase
Inflammatory bowel disease	Inflammatory bowel disease
Crohn's disease	Crohn's disease

25-FEB-2016 66

Disease/Disorder	
Ulcerative colitis	Ulcerative colitis
	Rectal bleeding
Coeliac disease	Coeliac disease
Sarcoidosis	Sarcoidosis
	Angiotensin converting enzyme increased
Asthma	Asthma
Allergies	Immune system disorders
	Allergic conditions
Auto immunity analyses	
Asthmatic crisis	Asthmatic crisis

8.1.9. Pregnancy

Female subjects who become pregnant after the vaccination may continue the study at the discretion of the investigator.

While pregnancy itself is not considered an AE or SAE, any adverse pregnancy outcome or complication or elective termination of a pregnancy for medical reasons will be recorded and reported as an AE or a SAE.

Note: The pregnancy itself should always be recorded on an Exposure During Pregnancy (EDP) form.

The following should always be considered as SAE and will be reported as described in Sections 8.3.1 and 8.3.2:

- Spontaneous pregnancy loss, including:
 - spontaneous abortion, (spontaneous pregnancy loss before/at 22 weeks of gestation)
 - ectopic and molar pregnancy
 - stillbirth (intrauterine death of foetus after 22 weeks of gestation).

Note: the 22 weeks cut-off in gestational age is based on WHO-ICD 10 noted in the EMA Guideline on pregnancy exposure [EMA, 2006]. It is recognized that national regulations might be different.

- Any early neonatal death (i.e. death of a live born infant occurring within the first 7 days of life).
- Any congenital anomaly or birth defect (as per [CDC MACDP] guidelines) identified in the offspring
 of a study subject (either during pregnancy, at birth or later) regardless of whether the foetus is
 delivered dead or alive. This includes anomalies identified by prenatal ultrasound, amniocentesis or
 examination of the products of conception after elective or spontaneous abortion.

Furthermore, any SAE occurring as a result of a post-study pregnancy AND considered by the investigator to be reasonably related to the investigational vaccine(s)/product(s) will be reported to Pfizer as described in Section 8.3.2. While the investigator is not obligated to actively seek this information from former study participants, he/she may learn of a pregnancy through spontaneous reporting.

8.2. Detecting and recording adverse events, serious adverse events and pregnancies

8.2.1. Time period for detecting and recording adverse events, serious adverse events and pregnancies

All AEs starting within 30 days following administration of the dose of study vaccine must be recorded into the appropriate section of the eCRF, irrespective of intensity or whether or not they are considered vaccination-related.

The time period for collecting and recording SAEs will begin at study start and will end 6 months following administration of the study vaccine dose for each subject. See Section 8.3 for instructions on reporting of SAEs.

All SAEs should be collected and recorded following administration of the study vaccine dose up to 6 months after.

SAEs that are related to the investigational vaccine and any event related to lack of vaccine efficacy will be collected and recorded from the time of the receipt of study vaccine until the subject is discharged from the study.

In addition to the above-mentioned reporting requirements and in order to fulfil international reporting obligations, SAEs that are related to study participation (i.e. protocol-mandated procedures, invasive tests, a change from existing therapy) will be collected and recorded from the time the subject consents to participate in the study until she/he is discharged from the study.

All AEs/SAEs leading to withdrawal from the study will be collected and recorded from study start.

The time period for collecting and recording pregnancies will begin from administration of the study vaccine dose and will end 30 days following administration of the study vaccine. See section 8.3 for instructions on reporting of pregnancies.

Occurrences of NOCIs (e.g. auto-immune disorders, asthma, type 1 diabetes, allergies) will be recorded from administration of the study vaccine dose until 6 months after administration of the study vaccine, whether or not they are considered to be possibly related to vaccine administration. Medical documentation of the events will be reported either as an unsolicited AE or as an SAE as appropriate in the eCRF.

Occurrences of GBS will be recorded from administration of the study vaccine dose until 6 months after administration of the study vaccine. Clinical details should be obtained as outlined in the 'Potential immune mediated disorders: standard questionnaires and list of preferred terms'. All occurrences of GBS have to be reported as SAEs.

An overview of the protocol-required reporting periods for AEs, SAEs, and pregnancies is given in Table 14.

Table 14 Reporting periods for adverse events, serious adverse events and pregnancies

	Persistence visits				Booster Vacc.1	4 days Post-vacc. ¹	31 days Post-vacc. ¹	ESFU	
Study activity	ICF signed	Visit 1 Month 78	Visit 2 Month 90	Visit 3 Month 102	Visit 4 Month 114	Visit 5 Month 126	Month 126+3days	Visit 6 Month 126+30 Days	Phone Contact Month 132
Recording of solicited local and general AEs									
Recording of unsolicited AEs									
Recording of NOCI ²									
Recording of All SAEs									
Recording of serious adverse events (SAEs) related to study vaccination and any event related to lack of vaccine efficacy since the previous visit. ^{3, 4}									
Recording of SAEs related to study participation ⁵									
Recording of GBS ⁶									
Recording of pregnancies ⁷									

- ¹ Vacc.: vaccination; Post-vacc.: post-vaccination.
- ² NOCI = new onset of chronic illness(es) (e.g. autoimmune disorders, asthma type I diabetes and allergies [a non-exhaustive list of NOCIs is provided in Table 13). These AEs are collected from Month 126 through Month 132.
- ³ Occurrence of meningococcal disease should be documented in the SAE report in the eCRF during the entire study period.
- ⁴ Including SAEs related to study vaccination and any event related to lack of vaccine efficacy occurring from the subject's last persistence visit to study entry in study MENACWY-TT-100 EXT: 027 Y6, 7, 8, 9, 10 will be recorded. Subject's parent(s)/LAR(s) will be questioned at study entry of study MENACWY-TT-100 whether any SAEs occurred during that time frame.
- ⁵ This will also include SAE(s) leading to the withdrawal of the subject from the study.
- ⁶ In the event of GBS, subjects should be contacted to obtain clinical details as outlined in the 'Potential immune mediated disorders: standard questionnaires and list of preferred terms'. All occurrences of GBS have to be reported as SAEs.
- ⁷ Pregnancies occurring between vaccination (Day 0) and 31 days after vaccination (Day 30) will be recorded. If, after having been vaccinated, a subject is found to have been pregnant at vaccination, the pregnancy will be recorded as an exclusion criterion. Subjects will be questioned at Month 132, 6 months after the booster vaccination, whether any unreported pregnancies occurred between Day 0 and Day 30 and these pregnancies will be recorded retrospectively.

25-FEB-2016 70

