4.2. Inclusion criteria for enrolment

Deviations from inclusion criteria are not allowed because they can potentially jeopardize the scientific integrity of the study, regulatory acceptability or subject safety. Therefore, adherence to the criteria as specified in the protocol is essential.

All subjects must satisfy the following criteria at study entry to the persistence phase:

- Subjects and/or subjects' parent(s)/LAR(s) who, in the opinion of the investigator, can and will comply with the requirements of the protocol (e.g. completion of the diary cards, return for follow-up visits).
- A male or female who has received a primary vaccination with the MenACWY-TT, *Meningitec* or *Mencevax ACWY* vaccines in study MenACWY-TT-027 (108658).
- In alignment with local laws and regulations, written informed consent obtained from parent(s)/LAR(s) of the subject and written informed assent obtained from the subject if the subject is less than 15 years of age, or written informed consent obtained from the subject if the subject has achieved the 15th birthday. The subjects ≥15 years of age at the time of enrolment will sign the informed consent form, even if the parent/ LAR previously signed the ICF before the subject reached the legal age of consent.
- Healthy subjects as established by medical history and history-directed physical examination before entering into the study.

All subjects must satisfy the following additional criteria prior to entry of the booster phase:

- Female subjects of non-childbearing potential may be enrolled in the study.
 - Non-childbearing potential is defined as pre-menarche, hysterectomy or bilateral ovariectomy.

35

Please refer to the glossary of terms for the definition of menarche.

- Male subjects able to father children and female subjects of childbearing potential (including females who have had tubal ligation) and at risk for pregnancy may be enrolled in the study, if the subject:
 - has practiced adequate contraception for 30 days prior to vaccination, and
 - has a negative pregnancy test on the day of vaccination (for females only), and
 - has agreed to continue adequate contraception during the entire treatment period and for 2 months after completion of the vaccination.

Please refer to the glossary of terms for the definition of adequate contraception.

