¹⁴ Pregnancies occurring between vaccination (Day 0) and 31 days after vaccination (Day 30) will be recorded. Subjects will be questioned at Month 132, 6 months after the booster vaccination, whether any unreported pregnancies occurred between Day 0 and Day 30 and these pregnancies will be recorded retrospectively. If, after having been vaccinated, a subject is found to have been pregnant at vaccination, the pregnancy will be recorded as an exclusion criterion.

¹⁵ To be completed for all subjects who are enrolled in the study

It is the investigator's responsibility to ensure that the intervals between visits/contacts are strictly followed. These intervals determine each subject's evaluability in the according-to-protocol (ATP) analyses. Subjects are able to participate in any study visit 1, 2, 3, 4, or 5 independent of other study visits, at their own or at their parent/LAR's discretion as applicable (e.g., it is possible that a subject comes to Visit 1 and Visit 3 but not Visit 2).

Table 5 presents the intervals between study visits.

Table 5 Intervals between study visits

Interval	Optimal length of interval ¹	Allowed interval ²
Dose 1 in primary vaccination study	78 months	78 months ± 12 weeks
MenACWY-TT-027 (108658)→Visit 1		
Dose 1 in primary vaccination study	90 months	90 months ± 12 weeks
MenACWY-TT-027 (108658)→Visit 2		
Dose 1 in primary vaccination study	102 months	102 months ± 12 weeks
MenACWY-TT-027 (108658)→Visit 3		
Dose 1 in primary vaccination study	114 months	114 months ± 12 weeks
MenACWY-TT-027 (108658) →Visit 4		
Dose 1 in primary vaccination study	126 months	126 months ± 12 weeks
MenACWY-TT-027 (108658)→Visit 5		
Visit 5 →Visit 6	30 days	21-48 days ³
Visit 5 → Phone Contact	6 months	180-210 days

¹ Whenever possible the investigator should arrange study visits within this interval.

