8.1.4. Exposure During Pregnancy

For both unapproved/unlicensed products and for marketed products, an exposure during pregnancy occurs if:

- A female becomes, or is found to be, pregnant either while receiving or having been exposed (eg, because of treatment or environmental exposure) to the study vaccine; or the female becomes or is found to be pregnant after discontinuing and/or being exposed to the study vaccine;
- 2. An example of environmental exposure would be a case involving direct contact with a Pfizer product in a pregnant woman (eg, a nurse reports that she is pregnant and has been exposed to chemotherapeutic products).
- 3. A male has been exposed (eg, because of treatment or environmental exposure) to the study vaccine prior to or around the time of conception and/or is exposed during his partner's pregnancy.

If a study subject or study subject's partner becomes or is found to be pregnant during the study subject's treatment with the study vaccine, the investigator must submit this information to the Pfizer drug safety unit on an SAE report form and an EDP supplemental form, regardless of whether an SAE has occurred. In addition, the investigator must submit information regarding environmental exposure to a Pfizer product in a pregnant woman (eg, a subject reports that she is pregnant and has been exposed to a cytotoxic product by inhalation or spillage) using the EDP supplemental form. This must be done irrespective of whether an AE has occurred and within 24 hours of awareness of the exposure. The information submitted should include the anticipated date of delivery (see below for information related to termination of pregnancy).

Follow-up is conducted to obtain general information on the pregnancy and its outcome for all EDP reports with an unknown outcome. The investigator will follow the pregnancy until completion (or until pregnancy termination) and notify Pfizer of the outcome as a follow-up to the initial EDP supplemental form. In the case of a live birth, the structural integrity of the neonate can be assessed at the time of birth. In the event of a termination, the reason(s) for termination should be specified and, if clinically possible, the structural integrity of the terminated fetus should be assessed by gross visual inspection (unless preprocedure test findings are conclusive for a congenital anomaly and the findings are reported).

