If the outcome of the pregnancy meets the criteria for an SAE (ie, ectopic pregnancy, spontaneous abortion, intrauterine fetal demise, neonatal death, or congenital anomaly [in a liveborn baby, a terminated fetus, an intrauterine fetal demise, or a neonatal death]), the investigator should follow the procedures for reporting SAEs.

Additional information about pregnancy outcomes that are reported as SAEs follows:

- Spontaneous abortion includes miscarriage and missed abortion;
- Neonatal deaths that occur within 1 month of birth should be reported, without regard to
 causality, as SAEs. In addition, infant deaths after 1 month should be reported as SAEs
 when the investigator assesses the infant death as related or possibly related to exposure
 to the study vaccine.

Additional information regarding the EDP may be requested by the investigator. Further follow-up of birth outcomes will be handled on a case-by-case basis (eg, follow-up on preterm infants to identify developmental delays). In the case of paternal exposure, the investigator will provide the study subject with the Pregnant Partner Release of Information Form to deliver to his partner. The investigator must document in the source documents that the subject was given the Pregnant Partner Release of Information Form to provide to his partner.

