for the time interval from the booster vaccination until Day 4 after booster

Pregnancies

for the time interval from the booster vaccination until Day 31 after booster

- All SAEs
- AEs/SAEs leading to withdrawal
- SAEs related to study vaccination or any event related to lack of vaccine efficacy
- SAEs related to study participation
- All unsolicited AEs

for the time interval from the booster vaccination until the end of study follow-up.

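### Scheduled pregnancy recording stops at Day 30, about half-way through the 2-month contraception period, and conflicts with open-ended pregnancy instructions elsewhere in the protocol (minor)

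*Protocol*

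**What the plan says.** **The precaution period.** For the booster phase, Protocol 4.2 admits females of childbearing potential at risk for pregnancy, and males able to father children, only if the subject "has agreed to continue adequate contraception during the entire treatment period and for 2 months after completion of the vaccination".

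**The recording window.** Protocol 8.2.1 is shorter: "The time period for collecting and recording pregnancies will begin from administration of the study vaccine dose and will end 30 days following administration". Table 4 footnote 14 (section 5.5) repeats it: "Pregnancies occurring between vaccination (Day 0) and 31 days after vaccination (Day 30) will be recorded". Table 14 footnote 7 says the same, and 8.3.1 ties prompt reporting of pregnancies to the period set in 8.2.

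**The last contact.** The Phone Contact is allowed 180-210 days after Visit 5 (Table 5). Its pregnancy question is restricted: "Subjects will be questioned at Month 132, 6 months after the booster vaccination, whether any unreported pregnancies occurred between Day 0 and Day 30". In Table 4 the pregnancy row is marked at Visits 5 and 6, and the Phone Contact cell is blank.

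**The listing.** SAP 7.2.3 lists pregnancies "for the time interval from the booster vaccination until Day 31 after booster". The SAE and unsolicited AE listings that follow it run to the end of follow-up.

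**Instructions without an end date.** Protocol 5.6.7 has subjects told to call at once about a known or suspected pregnancy in themselves or a partner. Section 8.1.4 counts as an exposure the case where "or the female becomes or is found to be pregnant after discontinuing and/or being exposed to the study vaccine". Section 8.1.9 requires an exposure-during-pregnancy (EDP) form for every pregnancy, 8.3.3 requires the EDP report within 24 hours of awareness, and 8.4.2 has pregnant subjects followed to outcome, with SAE outcomes reported whatever the SAE window.

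**The concern.** The protocol sets a period in which it wants pregnancy avoided, then asks about pregnancy for only the first half of it. A call that could cover the rest is already scheduled, but its question is confined to the early window.

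Two things are at stake. The first is ascertainment: pregnancies conceived in roughly Days 31-60 are identified only if somebody volunteers them, and outcome follow-up under 8.4.2 can start only once a pregnancy is known. The second is consistency: a site that learns of such a pregnancy reads in one set of sections that it lies outside the recording and prompt-reporting window, and in another that it must be reported within 24 hours. Sites may resolve this differently.

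**Working it through.** The plan states no figure to reproduce, so the check is day arithmetic followed by a comparison of the sections.

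**Inputs**
- Contraception period after the booster: 2 months (4.2). By calendar months this is L = 59 to 62 days.
- Recording window: Day 0 to Day 30 (8.2.1, Table 4 footnote 14, Table 14 footnote 7).
- Visit 6: 21-48 days after Visit 5. Phone Contact: 180-210 days after Visit 5 (both Table 5).

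**Days outside the recording window** = L - 30, and share = (L - 30)/L.
- L = 59: 29 days, 29/59 = 49.2%.
- L = 60: 30 days, 30/60 = 50.0%.
- L = 62: 32 days, 32/62 = 51.6%.

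**Do the scheduled contacts cover them?**
- Visit 6 does not. At its latest it is on Day 48, before the precaution period ends (48 < 59), and the recording rule stops at Day 30 in any case.
- The Phone Contact comes late enough: between 180 - 62 = 118 and 210 - 59 = 151 days after the precaution period ends. Its question nevertheless stops at Day 30.

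**Where a pregnancy would stand at that call.** For conception on Days 31 to 60, the time since conception is between 180 - 60 = 120 and 210 - 31 = 179 days, about 17 to 26 weeks. Most births would come after the last contact, and 8.2.2 does not oblige investigators to seek events in former participants.

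**A conception on Day 40, volunteered by the subject**
- 8.2.1 and Table 14 footnote 7: outside the recording window.
- 8.3.1: outside the period to which prompt reporting is tied.
- 5.6.7: the subject should already have called the site.
- 8.1.9: an EDP form is due. 8.3.3: the EDP report is due within 24 hours of awareness.
- 8.4.2: follow to outcome.
- SAP 7.2.3: not in the pregnancy listing. SAP 8.1 counts the booster as Day 0, so its Day 31 is at most one day later than the protocol's Day 30, which changes nothing here.

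**After the fix.** If recording and the Month 132 question cover the contraception period, the uncovered span falls from 29-32 days to 0, with no added contact.

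**The case against.** The strongest reply is that these pregnancies are not lost. Section 5.6.7 is a standing instruction to call, without an end date, and it includes partners. Sections 8.1.9 and 8.3.3 oblige the site to act once it knows. All SAEs are collected for 6 months after the dose, and 8.1.9 makes spontaneous loss, ectopic pregnancy, stillbirth and congenital anomaly SAEs, so a Day 40 conception lost before the call falls within SAE collection. This stands, and it limits the consequence. It does not supply a scheduled question, nor does it remove the conflict with 8.2.1, Table 14 and 8.3.1.

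Section 8.1.4 should not be pressed too hard either. Its definition for females is open-ended, but exposure through a male is bounded around conception or the partner's pregnancy, and its reporting duty for subjects and partners refers to pregnancy arising during treatment. The conflict rests more securely on 8.1.9 and 8.3.3.

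Nothing in the documents says that the recording window must equal the contraception period. A 30-day window may have been deliberate, though no reason is given, and a deliberate choice would still leave the sections at odds.

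Three stronger readings are tempting but unsupported:
- A reader might infer that a Visit 6 as early as Day 21 leaves early conceptions undetected. The retrospective question at Month 132 is there to pick those up.
- A reader might infer that the neonatal-death rules contradict each other: 8.1.4 has "Neonatal deaths that occur within 1 month of birth should be reported", while 8.1.9 names "Any early neonatal death (i.e. death of a live born infant occurring within the first 7 days of life". The shorter window lies inside the longer one, so a site can satisfy both, and aligning them is editorial.
- A reader might infer that the SAP listing misleads. It states its interval openly; it is simply short.

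**Conclusion.** The point holds as a minor one. Between 29 and 32 days of the protocol's own 59-62 day precaution period, about half, fall under no scheduled pregnancy question, and the 30-day limit in 8.2.1, Table 14 and 8.3.1 conflicts with the open-ended instructions in 5.6.7, 8.1.9 and 8.3.3. A reader might go further and conclude that pregnancies in this span are never captured. The documents do not support that: they can be reported, but only through volunteered information or site awareness.

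The size is given in days because no number of subjects or pregnancies can be derived. The documents give no sex split and no expected pregnancy count. The rule in 4.2 covers only those able to conceive or father a child, and half of the 326 planned at Year 10 (122 in ACWY<2 plus 41 in MenCCRM) were primed at 1 to <2 years, so are about 11.5-12.5 years old at Month 126.

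The calculation takes a month as a calendar month and dates a pregnancy from conception. No immunogenicity endpoint or sample size is affected, and no view is taken on which contraception period is right.

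**What to change.** - **Protocol 4.2, 5.6.7, 8.1.4, 8.1.9, 8.2.1, 8.3.1, 8.3.3, Table 4 footnote 14 and Table 14 footnote 7:** reconcile these so that one recording window applies, at least as long as whatever contraception period the protocol keeps, and so that prompt reporting follows it.
- **Month 132 call:** reword the existing question to ask about any pregnancy in the subject or partner since the booster.
- **Table 4:** mark the pregnancy row at the Phone Contact, which footnote 14 already requires.
- **SAP 7.2.3:** extend the pregnancy listing to the end of study follow-up, as for the SAE listing.
- **Editorial only:** align the neonatal-death wording in 8.1.4 and 8.1.9.

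The cost is wording in two documents and one reworded question in a call already made. The downside is a few more exposure reports to follow to outcome.
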